### 5.8.3. Exploratory Endpoints

#### 5.8.3.1. FACT-An Questionnaire

The FACT-An Questionnaire will be completed at Day 1 of Cycle 1 and every 4 subsequent cycles, End of Treatment, and End of Study visit. The FACT-An questionnaire contains 47 questions which are divided into the following subscales:

- Physical Well-Being (PWB) (7 questions: Item Score range 0 - 28)
- Social/Family Well-Being (SWB) (7 questions: Item Score range 0 - 28)
- Emotional Well-Being (EWB) (6 questions: Item Score range 0 - 24)
- Functional Well-Being (FWB) (7 questions: Item Score range 0 - 28)
- Anemia subscale (AnS) (20 questions: Item Score range 0 - 80)

Patients give individual responses to each question on a scale of 0 to 4 (0=Not at all; 1=A little bit; 2=Somewhat; 3=Quite a bit; 4=Very much). Item scores in the PWB and EWB subscales will be derived by subtracting the response value from 4. Similarly, all item scores in the AnS subscale except Item Codes An5, An7, BL4 and An13 will be derived by subtracting the response value from 4. Thus, a higher Item Score indicates a better quality of life. Subscale totals will be derived as follows:

$$\frac{\text{Sum of Item Scores} \times \text{Number of Items in Subscale}}{\text{Number of Items Answered}}$$

For example, if 6 questions are answered in the Physical Well-Being subscale and the Item scores sum to a total score of 18, then the subscale score will be  $(18 \times 7)/6 = 21$ .

If 50% or more of responses in any subscale are missing, the subscale score will be set to missing.

The following total scores will also be derived:

FACT-An Total Outcome Index (TOI) derived as: PWB + FWB + AnS  
(Score range 0 – 136)

FACT-G Total Score (FACT-G) derived as: PWB + SWB + EWB + FWB  
(Score range 0 – 108)

FACT-An Total Score (FACT-An) derived as: PWB + SWB + EWB + FWB + AnS  
(Score range 0 – 188)

If 20% or more of the responses that contribute to the FACT-G score are missing, the FACT-G score will be set to missing, i.e., at least 22 of the 27 items contributing to FACT-G must be present. Furthermore, FACT-An TOI, FACT-G and FACT-An scores should only be calculated if all component subscales have valid scores. If any subscale total is missing, the respective total scores to which the subscale contributes will also be set to missing.

Individual subscale scores and total scores will be summarized by visit. All derived subscale and total scores and all individual responses will be listed.

The association between FACT-An improvement and RBC-TI response will also be explored.

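### SAP 5.8.3.1 applies its 20% missing-item rule to FACT-G only, so the FACT-An total and TOI could be calculated with up to 43% and 44% of items missing, including on forms whose FACT-G is voided

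*SAP*

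**What the plan says.** SAP 5.8.3.1 scores the questionnaire in two layers.

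- **Subscales.** There are five: PWB, SWB, EWB, FWB and the anemia subscale (AnS). Each is prorated from the answered items to its full length. The limit is: "If 50% or more of responses in any subscale are missing, the subscale score will be set to missing".
- **Totals.** TOI is PWB + FWB + AnS. FACT-G is PWB + SWB + EWB + FWB. FACT-An is all five subscales added together. FACT-G alone has a second limit, void at 20% or more missing, which the SAP spells out as "at least 22 of the 27 items contributing to FACT-G must be present". The condition common to all three is "FACT-An TOI, FACT-G and FACT-An scores should only be calculated if all component subscales have valid scores", and a missing subscale makes every total that uses it missing.

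Subscale and total scores are summarized by visit, and all derived scores and individual responses are listed. The SAP also plans to explore the association between FACT-An improvement and RBC-TI response.

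**The concern.** By the SAP's own formulas, FACT-An equals FACT-G plus AnS. FACT-G is not itself one of the component subscales of FACT-An, however, so voiding FACT-G under the 20% rule does not void FACT-An. No other sentence in the SAP or protocol closes the gap.

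On such a form the plan judges the 27-item sum too incomplete to report, then adds that same prorated sum into FACT-An. Because all derived scores are listed, the suppressed FACT-G can be recovered as FACT-An minus AnS. TOI likewise has no overall completeness limit.

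What is at stake is how the quality-of-life tables read. FACT-G and FACT-An means at one visit can come from different sets of forms because of the rule mismatch, and a total can rest on much more proration than the SAP accepts for FACT-G. SAP 5.2 and 5.12.1 say missing data are generally not imputed. Proration is an exception to that, which is a reason to bound it in the same way across the totals.

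**Working it through.** **Inputs (all SAP 5.8.3.1).** PWB 7 items, SWB 7, EWB 6, FWB 7, AnS 20; sum 7 + 7 + 6 + 7 + 20 = 47, as stated. TOI has 7 + 7 + 20 = 34 items and FACT-G has 7 + 7 + 6 + 7 = 27.

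**Step 1: reproduce the SAP's own figure.** The largest m with m/27 below 0.20 is 5 (5/27 = 18.5%; 6/27 = 22.2% voids). So at least 27 − 5 = 22 items must be answered, which matches the SAP.

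**Step 2: largest number missing with each subscale still valid** (largest m with m/n below 0.50): PWB 3 of 7, SWB 3 of 7, EWB 2 of 6, FWB 3 of 7, AnS 9 of 20.

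**Step 3: add these up for each total, and compare with a 20% rule.**

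| Total | Items | Most missing, subscale rule only | Most missing, 20% rule | Fewest answered, 20% rule |
|---|---|---|---|---|
| FACT-G | 27 | 3 + 3 + 2 + 3 = 11 (40.7%) | 5 (18.5%) | 22 |
| TOI | 34 | 3 + 3 + 9 = 15 (44.1%) | 6 (17.6%) | 28 |
| FACT-An | 47 | 3 + 3 + 2 + 3 + 9 = 20 (42.6%) | 9 (19.1%) | 38 |

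As the SAP stands, FACT-G is held to the 20% column, while TOI and FACT-An are held only to the subscale column.

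**Step 4: forms on which the rules disagree.** With every subscale valid, FACT-G can have 0 to 11 items missing. It is void at 6 to 11, and FACT-An and TOI are still calculated. Both maxima in Step 3 fall on such forms, because 3 PWB and 3 FWB items missing already make 6 of 27.

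**Step 5: test the candidate fixes for FACT-An.**

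- *At least 38 of 47 answered, alone.* Take a form with 3 PWB and 3 SWB items blank and the rest complete. FACT-G is missing 6/27 = 22.2% and is void. FACT-An is missing 6/47 = 12.8% and is still calculated. The mismatch survives.
- *FACT-G valid, alone.* Up to 5 FACT-G items and 9 AnS items may be missing: 14/47 = 29.8%. The mismatch goes, but completeness is still below the FACT-G standard.
- *Both together.* At most 5 of 27 FACT-G items and at most 9 of 47 items overall may be missing. Both problems go.

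For TOI, a valid FACT-G would still allow 5 + 9 = 14 of 34 missing (41.2%), so TOI needs its own 28-of-34 limit.

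**The case against.** - **The totals are not unprotected.** Every component subscale must be more than half answered. The documents nowhere say that FACT-An or TOI must be 80% complete, so extending the limit to them is an argument from consistency. Dropping a form instead of prorating it is a trade-off. This stands, and it is why stating a rationale for the split would also be acceptable.
- **Different denominators are normal.** A form with FACT-G complete and half of AnS missing gives FACT-G without FACT-An under any sensible rule, and SAP 5.2 reports n for each summary. This also stands. What it does not explain is reporting a sum that contains a component the same section has voided.
- **The impact is small.** Quality of life is exploratory, all summaries are descriptive, and individual responses are listed, so a stricter rule could be applied afterwards. This stands and sets the priority.

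A reader might go further and infer that totals will in fact be reported with 43 to 44% of items missing. The documents do not support that. These are ceilings, reached only when every contributing subscale is at its limit on the same form, and no missingness rates are given.

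Nor do the documents show that the RBC-TI association rests on heavily prorated scores: the SAP does not say whether FACT-An improvement there means the total, the TOI or a subscale. They also name no principal quality-of-life score, so FACT-An cannot be called the headline measure.

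**Conclusion.** The inconsistency is real and follows from the SAP's text alone. FACT-G tolerates 5 of 27 items missing (19%), while FACT-An could be calculated with 20 of 47 missing (43%) and TOI with 15 of 34 (44%). Forms with 6 to 11 FACT-G items missing and all subscales valid lose FACT-G but keep the same prorated sum inside FACT-An.

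The counts rest only on the item numbers and thresholds in SAP 5.8.3.1. How many forms are affected is unknown; that the share is small is an assumption. The primary safety objective and the secondary efficacy endpoints are untouched. It is a cheap improvement.

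**What to change.** In SAP 5.8.3.1, keep the subscale rule and add:

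- FACT-An total is missing if FACT-G is missing under its 20% rule, or if 20% or more of the 47 items are missing (at least 38 answered required).
- TOI is missing if 20% or more of its 34 items are missing (at least 28 answered required).

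TOI may still be calculated on some forms with FACT-G void, for example with 3 PWB and 3 FWB items blank (6/34 = 17.6%). That is not contradictory, because TOI does not contain the full 27-item sum.

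The cost is one or two sentences, best added before the SAP is signed off, and a few forms that lose a total score. If the sponsor prefers the present split, the alternative is to state the reason and report how many forms at each visit have FACT-G void but FACT-An calculated.

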#### **5.8.4. Subgroup Analyses**

Subgroup analyses of the efficacy endpoints will be performed for the following baseline parameters:

- RS status (positive or negative),
- SF3B1 mutation status (mutated or wild type)
- Splicing factor mutation status (mutated or wild type)
- Baseline EPO level ( $\leq$  or  $>100$ ,  $\leq$  or  $>200$ ;  $\leq$  or  $>500$ )
- Baseline bone marrow blasts ( $< 5\%$  or  $\geq 5\%$ )
- IPSS risk group (low, Int-1, Int-2, or high)
- IPSS-R risk group (very low, low, intermediate, high, very high)

Logistic regression analysis will be performed to evaluate the effect of following prognostic factors on the IWG HI-E response and RBC-TI individually.

- IPSS risk group (low vs Int-1/Int-2/high)
- Baseline EPO (continuous)
- Baseline EPO level ( $\leq 100$  vs.  $> 100$  IU/L)
- Baseline EPO level ( $\leq 200$  vs.  $> 200$  IU/L)
- Prior ICT (Yes vs. No)
- Prior ESA (Yes vs. No)
- RS status (positive vs. negative),
- SF3B1 mutation status (mutated vs wild type)

Multivariable logistic regression analysis with backward selection will be performed to evaluate the association of association between baseline factors and IWG HI-E and RBC-TI response.

### 5.8.5. Safety Analyses

The safety endpoints will be summarized based on the Safety Population. The safety endpoints include the incidence of treatment emergent adverse events, changes in laboratory tests, vital signs and ECG's.

Adverse events (AEs) will be coded using MedDRA Version 20.0. Severity of AEs will be coded using National Cancer Institute Common Toxicity Criteria for Adverse Events version 4.0 (NCI-CTCAE v4.0).

### 5.8.6. Adverse Events

All AEs and SAEs occurring after the Study A536-03 (for patients without interruption) or Study A536-05 (for patients with interruption) Cycle 1 Day 1 until approximately 2 months after the last study drug administration (PTFU visit) are to be reported and documented on the AE CRF.

Treatment emergent adverse events (TEAE) are defined as:

- AE starting or worsening from the first date of study drug;
- AE occurs on the first date of study drug and the onset check box is marked “Onset after first dose of study drug”;
- AE with a missing start date and a non-missing stop date on or after the first dose of study drug;
- AE with both a missing start and stop date.

A drug-related TEAE is defined as any TEAE related to the study medication as assessed by the investigator or with missing assessment of the causal relationship.

The following summaries will also be presented:

- Number and percentage of patients reporting each AE, categorized by SOC and PT
- Number and percentage of patients reporting each AE experienced by  $\geq 5\%$  of patients in all patients by PT
- Number and percentage of patients reporting SAE, categorized by SOC and PT
- Number and percentage of patients reporting Grade  $\geq 3$  AE, categorized by SOC and PT
- Number and percentage of patients reporting related AE, categorized by SOC and PT
- Number and percentage of patients reporting AE leading to drug withdrawal, categorized by SOC and PT
- Number and percentage of patients reporting AEs of interest by cycle

Note that counting will be by patient, not event, and patients are only counted once within each SOC or preferred term. If a patient has the same AE at more than one severity, or with more

than one relationship to study drug, the most severe rating or the stronger causal relationship to study drug will be given precedence. Any missing severity, causality, or outcome will not be imputed and classed as unknown.

All AEs will be listed. The following listings will also be provided: 1) patients with SAEs; 2) patients with Grade  $\geq 3$  AEs; 3) patients with AEs leading to discontinuation.; and 4) death.

### **5.8.7. Laboratory Evaluations**

Results from the following laboratory parameters, recorded at their respective time points will be summarized by time point:

**Hematology** (Screening, Day 1 of each cycle, End of Treatment, Post Treatment Follow Up and End of Study): RBC, white blood cell (WBC) with differential, hemoglobin, hematocrit, reticulocyte count, platelet count, mean corpuscular volume (MCV), mean corpuscular hemoglobin (MCH), mean corpuscular hemoglobin concentration (MCHC), red blood cell distribution width (RDW), and nucleated RBCs (nRBCs)

**Chemistry** (Screening, Day 1 of Cycle 1 and Day 1 of every other subsequent cycles, End of Treatment and End of Study): Sodium, potassium, aspartate aminotransferase (AST), alanine aminotransferase (ALT), lactate dehydrogenase (LDH), total bilirubin, direct bilirubin, alkaline phosphatase, blood urea nitrogen (BUN)/urea, creatinine, gamma-glutamyl transpeptidase (GGT), calcium, phosphorus, glucose, amylase, lipase, total protein, albumin, and uric acid

**Urine Analysis** (Day 1 of Cycle 1 and every 4 subsequent cycles, End of Treatment and End of Study): pH, specific gravity, protein, glucose, ketones, blood, leukocyte esterase, nitrite, microscopic examination (if performed)

**Urine Chemistry** (Day 1 of Cycle 1 and every 4 subsequent cycles, End of Treatment and End of Study): Microalbumin and creatinine; albumin/creatinine ratio

Categorical and numeric variables will be presented separately. Actual values and changes in hematology and biochemistry laboratory values from baseline will be summarized by time point. Shift tables for the hematology and biochemistry laboratory parameters comparing values above, within and below the normal reference range at baseline to the end of treatment visit will be presented using standard reference ranges.

Peripheral blood smears are taken at Screening, Day 1 of Cycle 1 and every 4 subsequent cycles, and at the end of treatment visit. These data will be listed only.

All laboratory values will be listed for all patients.

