7.3. Summary of Clinical Experience

The safety, tolerability, pharmacokinetics (PK), and pharmacodynamics (PD) effects of ACE-536 was evaluated in healthy postmenopausal women in a phase 1, randomized, double-blind, placebo-controlled, multiple ascending dose study (Study A536-02). The primary objective of the study was to evaluate the safety and tolerability of ACE-536 in this population. Secondary objectives of the study are to examine the PK parameters and PD effects of ACE-536.

A total of 32 subjects were enrolled. Eligible subjects were healthy, postmenopausal women, 45-75 years old. The anticipated PD effect was an increase in plasma hemoglobin level. Screening and baseline hemoglobin values had to be between 11.0 and 14.5 g/dL, inclusive, to mitigate the risk of substantial excursions above the normal range. Sequential cohorts of 8 subjects each were randomized to receive either ACE-536 (n=6) or placebo (n=2) administered as a SC injection on Day 1 and Day 15. Each subject was to be followed for 112 days (16 weeks) after receiving their last dose of ACE-536 or placebo. The following dose levels were evaluated: 0.0625, 0.125, and 0.25 mg/kg.

ACE-536 administered every 2 weeks by subcutaneous (SC) injection for one or two doses at dose levels of 0.0625, 0.125 or 0.25 mg/kg was generally safe and well-tolerated in healthy postmenopausal female subjects. No serious or severe adverse events (AE) were reported. The majority of AEs were considered mild in severity. AEs that were considered at least possibly drug-related across ACE-536 dose groups included injection site hemorrhage (3 subjects), injection site macule (2 subjects), and dry skin, macule, hyperesthesia, muscle spasms, myalgia, generalized pruritus, and papular rash (1 subject each). Injection site pain was reported in one placebo-treated subject.

PK results indicated mean area under the concentration-time curve (AUC) and maximum concentration (C_{max}) values increased in a dose-proportional manner with ACE-536 dose level; mean time to maximum concentration (T_{max}) ranged from 7.0 to 9.8 days, and mean $T_{1/2}$ ranged from 14.9 to 16.2 days after the first dose. These PK results support intermittent SC dosing of ACE-536 in future studies, e.g., every 3 weeks.

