9.2. Selection of Study Population

9.2.1. Inclusion Criteria

All patients must meet the following criteria:

1. Completion of the treatment period in the base study A536-03.
2. Females of child bearing potential (defined as sexually mature women who have not undergone hysterectomy or bilateral oophorectomy, or are not naturally postmenopausal ≥ 24 consecutive months) must have negative urine or blood pregnancy test prior to enrollment and use adequate birth control methods (abstinence, oral contraceptives, barrier method with spermicide, or surgical sterilization) during study participation and for 12 weeks following the last dose of ACE-536. Males must agree to use a latex condom during any sexual contact with females of child-bearing potential while participating in the study and for 12 weeks following the last dose of ACE-536, even if he has undergone a successful vasectomy. Patients must be counseled concerning measures to be used to prevent pregnancy and potential toxicities prior to dosing with ACE-536.
3. Patient is able to adhere to the study visit schedule, understand and comply with all protocol requirements.
4. Patient understands and is able to provide written informed consent.

Patients with treatment interruption (defined as patients who completed the A536-03 EOS visit) must also meet the following criteria:

5. Documented diagnosis of idiopathic/de novo MDS or non-proliferative chronic myelomonocytic leukemia (CMML) according to WHO criteria¹⁶ (white blood count [WBC] $< 13,000/\mu\text{L}$) that meets International Prognostic Scoring System (IPSS) classification ([Appendix 2](#)) of low or intermediate-1 risk disease as determined by microscopic and standard cytogenetic analyses of the bone marrow and peripheral complete blood count (CBC) obtained during screening;
6. Anemia defined as:

- Mean hemoglobin concentration < 10.0 g/dL of 2 measurements (one performed within one day prior to Cycle 1 Day 1 and the other performed 7-28 days prior to Cycle 1 Day 1) for NTD patients (defined as having received < 4 units of RBCs within 8 weeks prior to Cycle 1 Day 1), OR
- Transfusion Dependent (TD), defined as having received \geq 4 units of RBCs within 8 weeks prior to Cycle 1 Day 1.

7. Platelet count ($\geq 30 \times 10^9/L$).
8. ECOG performance status of 0, 1, or 2 (if related to anemia).

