14. ASSESSMENT OF SAFETY

14.1. Adverse Event Definitions

Adverse Event

An AE is any untoward medical occurrence in a patient or clinical investigation subject administered a study drug, which does not necessarily have a causal relationship with this treatment. An AE can therefore be any unfavorable and unintended sign (including an abnormal laboratory finding), symptom, or disease temporally associated with the use of the study drug whether or not it is considered related to the study drug.

Abnormal laboratory and other abnormal investigational findings (e.g. physical exam, ECG) should not be reported as AEs unless they are associated with clinical signs and symptoms, lead to treatment discontinuation or are otherwise considered clinically relevant by the investigator. In cases of surgical or diagnostic procedures, the condition/illness leading to such a procedure is considered as the AE rather than the procedure itself. In case of a fatality, the cause of death is considered as the AE, and the death is considered as its outcome.

Unexpected Adverse Events

An unexpected AE is an AE that is not described in nature or severity in the IB.

Events Not to Be Considered as Adverse Events

Pre-existing medical conditions/signs/symptoms present before the Screening period (from study A536-03 for patients without treatment interruption; from study A536-05 for patients with treatment interruption) that do not worsen in severity or frequency during the study are defined as Baseline Medical Conditions, and are not to be considered AEs. Anticipated day-to-day fluctuations of pre-existing conditions, including the disease under study, that do not represent a clinically significant exacerbation or worsening need not be considered adverse events.

Serious Adverse Event

A SAE is any AE, occurring at any dose level/regimen and regardless of causality that:

- Results in death.
- Is life-threatening: Life-threatening means that the patient was at immediate risk of death from the reaction as it occurred (i.e., it does not include a reaction which hypothetically might have caused death had it occurred in a more severe form).
- Requires inpatient hospitalization or prolongation of existing hospitalization; however, a hospitalization for an elective procedure will not be considered a SAE.
- Results in persistent or significant disability/incapacity.
- Is a congenital anomaly/birth defect.

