**End of Treatment (EOT)**

Procedures and evaluations for the end of treatment visit should be performed 28 days ( $\pm 7$  days) after the last dose of ACE-536.

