## **5.2. General Considerations**

Unless otherwise noted, continuous data will be summarized with the following descriptive statistics: number of observations (n), mean, standard deviation (STD), median, minimum and maximum. Categorical data will be summarized with frequencies (n) and percentages (%). In cases where missing data cause percentages not to sum to 100, a missing data row will be provided. Percentages will use column totals as the denominator unless otherwise indicated. For time to event variables, the Kaplan-Meier curves will be presented if the number of patients is more than 5.

All study data will be included in study data listings. Missing data will generally not be imputed, unless otherwise stated.

Data summaries may also be presented for LTB and HTB patients separately as specified. All summaries will be descriptive. No formal hypothesis testing is planned.

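### The only per-patient laboratory safety summary in SAP 5.8.7 is a three-category shift from baseline to EOT, which cannot show decline in counts already low and does not record abnormalities that resolved

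*SAP*

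**What the plan says.** SAP 5.8.7 defines one kind of laboratory shift table, "comparing values above, within and below the normal reference range at baseline to the end of treatment visit". The same section also plans that "Actual values and changes in hematology and biochemistry laboratory values from baseline will be summarized by time point", and SAP 5.2 sets the statistics for continuous data as "number of observations (n), mean, standard deviation (STD), median, minimum and maximum". Listings are complete: "All laboratory values will be listed for all patients".

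SAP 5.8.5 applies NCI-CTCAE v4.0 to the severity of AEs. Neither document applies it to laboratory values or plans a worst-on-treatment laboratory summary. Protocol 15.2.2 promises descriptive statistics and shift tables where suitable, without fixing categories or visits.

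On timing, SAP 5.1 states: "Procedures and evaluations for the end of treatment visit should be performed 28 days" after the last dose, with a 7-day window. Protocol Section 2 (schedule footnote 17) and 12.3 add that patients who stop early have EOT when they discontinue.

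On the route into the AE data, Protocol 14.1 says that abnormal laboratory findings "should not be reported as AEs unless they are associated with clinical signs and symptoms", cause treatment to stop, or are thought clinically relevant by the investigator. Protocol 14.5 requires clinically relevant laboratory changes to be recorded as AEs.

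**The concern.** Long-term safety is the primary objective, and SAP 5.8.5 names changes in laboratory tests as a safety endpoint. A reader of the final report will want to know how many patients developed new or deeper cytopenia, or an abnormal chemistry result, during up to five years of dosing. The planned table has two limits.

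- **Range.** This population enters with low counts. Non-transfusion-dependent patients with treatment interruption must have "Mean hemoglobin concentration < 10.0 g/dL of 2 measurements" (Protocol 9.2.1), and patients with interruption may enter with platelets from 30 x 10^9/L. SAP 5.8.2.4 itself provides for baseline platelets below 100 and below 20 x 10^9/L, and for neutrophils below 1.0 x 10^9/L.
- **Timing.** One visit stands for the whole treatment period.

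The plan is also uneven. SAP 5.8.2.4 credits platelet and neutrophil improvement in any rolling 8-week window on treatment, while the shift table looks for worsening only at the last visit.

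**Working it through.** The plan states no figure to reproduce. The check has three parts.

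**1. Range.** The documents give no reference ranges, so lower limits of normal (LLN) are assumed: 100, 130 or 150 x 10^9/L for platelets (upper limit 450), and 10, 12 or 13.5 g/dL for hemoglobin (upper limit 17.5). Values are constructed.

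| Test | Baseline | Worst | EOT | Planned shift | Baseline to worst, same categories |
|---|---|---|---|---|---|
| Platelets | 90 | 15 | 15 | below to below | below to below |
| Platelets | 35 | 8 | 8 | below to below | below to below |
| Platelets | 95 | 10 | 92 | below to below | below to below |
| Platelets | 200 | 20 | 210 | within to within | within to below |
| Hemoglobin | 9.5 | 6.0 | 6.0 | below to below | below to below |

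The results are the same at every assumed LLN. The reason is general: if baseline is under the LLN, any lower value is under it too. The last column shows that taking the worst value in the same three categories repairs only the timing limit. The range limit needs graded categories.

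**2. Timing.** The cap is 87 cycles (Protocol 9.1). SAP 5.8.7 places hematology at Day 1 of each cycle and chemistry at every other cycle, plus EOT. Counting A536-05 visits after C1D1, through EOT, for a full course:

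- Hematology: C2D1 to C87D1 is 87 - 1 = 86 visits, plus EOT = 87. Share used: 1/87 = 1.1%.
- Chemistry: C3D1 to C87D1 in steps of two is (87 - 3)/2 + 1 = 43 visits, plus EOT = 44. Share used: 1/44 = 2.3%.
- C87D1 falls (87 - 1) x 21 = 1806 days after C1D1 without delays, so a resolved abnormality can precede EOT by years.

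Shorter courses have fewer visits. Patients without interruption use the A536-03 baseline (SAP 5.1), so they also have A536-03 results that are not counted here. A patient with no EOT sample has no pair, and SAP 5.12.1 does not impute missing laboratory values.

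**3. What else would show the event.**

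- *By-visit statistics.* The minimum shows the most extreme value at a visit. It is 15 whether one patient or ten fell to 15.
- *Listings.* They hold every value but count nothing.
- *AE tables (SAP 5.8.6).* They count by patient at the highest severity, but only for changes the investigator reported. Protocol 14.1 also lets expected fluctuation of the disease under study go unreported unless it is a clinically significant worsening.
- *Other per-patient laboratory outputs.* The HI-P and HI-N rates count improvement only. The ferritin shift in SAP 5.8.2.6 is again baseline to EOT.

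**The case against.** The strongest reply is that the shift table does not stand alone.

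- **AE tables.** Clinically relevant laboratory changes must be recorded as AEs, and SAP 5.8.6 tabulates Grade 3 or higher AEs by patient. A platelet fall from 90 to 15 would very probably be reported. This stands for extreme cases. It does not give a count based on the measured values, and smaller declines in patients with known MDS remain a matter of judgement.
- **Dose holds.** A reader might infer that a laboratory toxicity that led to a hold and then resolved would go unseen. The documents do not support that. The hold rule for non-hematologic toxicity in Protocol 10.8 presupposes a Grade 3 or higher AE at least possibly related to study drug. Such an event enters the AE tables, and SAP 5.6 also counts patients with dose delays and reductions.
- **Early discontinuation.** Patients who stop early have EOT at that time, so for someone stopped for toxicity the table may well capture the event. This stands, and it limits the timing problem to abnormalities that resolved before EOT.
- **By-visit summaries.** They include median, minimum and maximum as well as means, so extreme values are visible. This stands, but it shows that an extreme occurred, not how many patients worsened.
- **Half-life.** A reader might infer from Protocol 7.3 that drug effect has faded by EOT. Those data come from healthy postmenopausal women given one or two doses of at most 0.25 mg/kg, and neither limit of the table depends on them.
- **Worst-grade hemoglobin.** In transfused patients with anemia and no control arm, it partly reflects disease and transfusion timing. This stands, and the fix must allow for it.

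No protocol commitment is broken, and no hypothesis test depends on this table.

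**Conclusion.** The point holds as a gap in the laboratory safety summary: the plan contains no per-patient count of laboratory worsening on treatment. The range limit follows from the table's definition for any test below range at baseline. That should be hemoglobin in most patients, and platelets and neutrophils in those who start low. The documents fix entry hemoglobin only for non-transfusion-dependent patients with interruption, so *most* is an assumption, as is an LLN of at least 10 g/dL. Patients who start within range can still shift to below at EOT. The timing limit applies to every test: 1 of up to 87 hematology results and 1 of 44 chemistry results over a full course.

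A reader might infer that the safety analysis as a whole misses these events, or that reported toxicity rates will be too low by some amount. The documents do not support either. Other outputs cover part of the gap, and no laboratory event rates are given from which to compute a bias. The change is worth making because the primary objective is long-term safety and the cost is small.

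**What to change.** In SAP 5.8.7, add to the planned tables:

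- a shift from baseline NCI-CTCAE v4.0 grade to worst on-treatment grade for gradable hematology and chemistry tests, including unscheduled visits, with the number of patients worsening to Grade 3 or higher;
- for tests without a grade, worst-high and worst-low values against the normal range.

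State the period: from the first dose in A536-03 for patients without interruption and the first dose in A536-05 for patients with interruption, through EOT. This agrees with SAP 4.1 and 5.1. For hemoglobin, apply the exclusion of values within 7 days after an RBC transfusion that SAP 5.8 already uses for efficacy, and present results separately for LTB and HTB patients. Keep the baseline-to-EOT shift as a supplementary table.

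The cost is SAP wording and standard programming. No new data are needed, and Protocol 15.2.2 is general enough that no protocol amendment is required. The downside is a table that will look somewhat less favorable and is more sensitive to isolated outliers.
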